3.3 Method of Treatment Assignment and Randomization

This is a single arm study.

3.4 Treatment Masking (Blinding)

This is an open-label study.

4. ANALYSIS AND REPORTING

Interim analyses for fertility per NHL subtype are the responsibility of the sponsor; XXXXXXXXXX

CONFIDENTIAL

03 April 2019

██████████ will not be involved in formal interim analyses (please refer to Section 5 for further details). Decisions made at interim analysis will be described in the CSR.

4.1 Final Analysis

The analyses identified in the protocol and in this SAP will be performed after a database cutoff foreseen in July 2015. At that time, all patients will have completed the main treatment period (that is, up to 3 cycles of MOR00208 therapy), though some patients will still be receiving maintenance treatment and few other patients may be in the follow-up phase (for survival only, without maintenance treatment).

Based on the present SAP, analyses at a later point in time may be conducted, e.g., for regulatory interactions, following database lock.

Further analyses will be done after the last patient has completed the end of study visit, all data have been processed and the database has been locked. Those analyses will be used to prepare an addendum to the CSR. In addition, no database may be locked or analyses completed until this SAP has been approved and signed off by all responsible parties.

All study results will be made available to MorphoSys AG following database lock and prior to completion of the final CSR.

MorphoSys will perform further exploratory analyses to investigate correlations between different biomarker and response variables.

Any post-hoc, exploratory analyses completed to support planned study analyses, which were not identified in this SAP, will be documented and reported in appendices to the CSR, but will not necessitate an update of the final SAP. Any results from these unplanned analyses (post-hoc) will also be clearly identified in the text of the CSR.

4.2 Final Pharmacokinetic Analysis

The final PK analysis will be performed on data from the clinical database combined with the concentration data from the bioanalytical lab after the database has been locked.

PK Input Files will be created using SAS[®] software (version 9.3 or later) from the serum concentrations reported by the bioanalytical lab combined with the dosing and sampling information from the clinical database after the database has been locked. Actual elapsed time from dose to sampling time will be used for all parameter estimation but mean concentration data will be presented in tables and figures using scheduled sampling times. Any concentration values outside acceptable time windows will be excluded from those summary statistics (see

section 10.3.2 for details). For patients receiving maintenance treatment after cycle 3, the FU1, FU2 and FU3 visits will be excluded from PK summary statistics, since the concentrations of MOR00208 at the FU1, FU2 and FU3 visits may be influenced by additional MOR00208 doses in maintenance treatment.

The PK analysis will be conducted using the Phoenix WinNonlin[®] version 6.3 or later software from Pharsight, Cary, North Carolina. The PK tables, listings, and figures will also be produced in SAS. Any PK tables that involve inference testing will be performed by statisticians using SAS software.

The AUC_{0-last} will be produced from the first dose including samples up to the 24-hour post-infusion sample drawn just before the 2nd infusion. The last dose will provide as many as 4 samples starting at the sample drawn at Cycle 3 Day 28 and including the 3 follow-up visit samples. These samples from the last dose will be used to estimate the terminal elimination rate and its associated half-life.

5. SAMPLE SIZE DETERMINATION

A two-stage design is used to minimize exposure of NHL subtypes not showing responsiveness to MOR00208. No formal sample size estimations for determination of futility were computed for Stage 1. The number of patients to be used in this stage was determined to be the minimum number needed to adequately determine futility in any specific NHL subtype. The entire study will enroll between 40 to 120 patients, dependent upon patient response in each subtype in Stage 1.

Stage 1: Approximately 40 patients, an equal number of patients will be enrolled per NHL subtype:

- FL: 10 patients
- DLBCL: 10 patients
- MCL: 10 patients
- other indolent NHL: 10 patients

Observing less than two responses (at least PR) in 10 patients in any NHL subtype will be the criterion for discontinuing evaluation of MOR00208 in that NHL subtype. If the study drug is effective with a true ORR of 30%, the probability to stop for futility after the first stage for a specific NHL subtype is only 14.9%.

Stage 2: For those NHL subtypes with two or more responders, an additional 20 patients will be

enrolled for a total of 30 patients per subtype. Assuming that the true ORR of any NHL type is 30% and that the number of responses actually observed in the study corresponds to the expected number of responses (9 responses), N=30 would yield a lower limit of the 95% confidence interval for the ORR of 14.7%. Up to a maximum of 80 additional patients, an equal number of patients will be enrolled per “responding” NHL subtype. Some of the cohorts may have been stopped for futility after Stage 1:

- FL: 20 patients
- DLBCL: 20 patients
- MCL: 20 patients
- other indolent NHL: 20 patients

Approximately 25 to 30 centres in the United States of America and Europe are planned.

6. ANALYSIS POPULATIONS

The following analysis populations will be defined:

- Intent-to-treat (ITT) Population: Consists of all patients who received at least one dose of study drug. Patients without any post baseline assessment of NHL response will be included as non responders.
- Safety Population: Consists of all patients who received at least one dose of study drug.
- Pharmacokinetic (PK) Population: The Pharmacokinetic Population will include all patients who have at least one quantifiable serum MOR00208 concentration. (PK parameters will be calculated as data permit.)

Please note that the definition of the PK population differs slightly from that in the protocol: see section 12.

7. GENERAL ISSUES FOR STATISTICAL ANALYSIS

7.1 General Statistical Methodology

Tables for disposition of patients and study discontinuations (see Section 8.1) will be produced for all patients enrolled. The Safety Population will be used for safety analysis and to analyze immunogenicity. The ITT Population will be used to analyze pharmacodynamic endpoints. Summaries for the analysis of response by investigator and radiology central reader will be provided for the ITT Population. Pharmacokinetic summaries will be presented for the

Pharmacokinetic Population.

If not specified otherwise, all statistical summaries will be presented by NHL subtype, for the combined subtype of FL and other indolent NHL, and overall.

Tabulations of summary statistics, graphical presentations, and statistical analyses will be performed using SAS software, Version 9.3 or later.

Continuous, quantitative variable summaries will include the number of patients (N) (with non-missing values), mean, standard deviation, median, minimum and maximum. Some of the descriptive summaries (as specified in the subsequent sections) will additionally include the 95%-confidence interval for the mean (absolute) change from baseline. The confidence interval will be calculated based on the quantiles of the t-distribution assuming normal distribution of the data. Moreover, some of the descriptive summaries (as specified in subsequent chapters) will include the 95%-confidence interval for the median (absolute or percentage) change from baseline. The 95%-confidence interval for the median will be calculated without any assumption on the distribution of the data (nonparametric confidence interval). For this calculation the SAS option CIQUANTDF in proc UNIVARIATE may be used.

Categorical, qualitative variable summaries will include the frequency and percentage of patients who are in the particular category.

For time durations in days that need to be converted to months, the number of days will be divided by factor 30.4375. For time durations in days that need to be converted to years, the number of days will be divided by factor 365.25.

Unless otherwise specified, Baseline is the last observation before the start of the study treatment, which is expected to be the Baseline Visit on Day 1, or Screening or any other unscheduled visits before the start of the study drug administration, if Baseline, Day 1 data are not available. For data such as CD16 expression on NK cells which is only recorded at Screening the Screening value will be the Baseline value, if the Screening value is missing then the baseline value will also be missing.

All data obtained on the eCRF and entered into the database will be provided in separate data listings showing individual patient values. The planning and reporting of statistical analyses will be carried out as described in the [REDACTED] SOPs.

Any patient who withdraws from the study will be analyzed with the data available. Imputation of missing values will not be performed, unless specified in the relevant sections of the SAP.

7.2 Handling of Missing Data for PK Analysis

Missing data can be from patients who drop out and do not complete the study or from serum concentration data that are not reported by the bioanalytical lab due to technical issues.

Handling of both of these situations is described in this section.

Any patient who withdraws from the study will be evaluated for inclusion in the PK analysis based on the PK data available.

A distinction is made between a missing serum concentration due to failure to deliver the sample to the bioanalytical lab for assay, a serum concentration that was not reported by the bioanalytical lab due to a failure of the assay or handling, and a matrix concentration that is reported as being below limit of quantifiable (BLQ) of the assay. Samples that are reported with measurable concentrations are included in the PK analysis. Samples that are reported as BLQ are either assigned zero or missing depending on their location in the profile (process explained in Section 10.3.2) as this affects the calculation of AUCs. Samples that are either not reported or reported as missing will be reported as missing in the analysis.

7.3 Derived and Computed Variables

The following derived and computed variables for immunogenicity, efficacy and exposure data have been initially identified as important for the statistical analysis. Additional variables may be required. The SAP will not be amended for additional variables that are not related to the primary or secondary endpoints. Any additional derived or computed variables will be identified and documented in the SAS programs that create the analysis files. If the SAP is not amended, further derivations related to primary and secondary target variables will be described in the CSR.

7.3.1 Previous NHL therapy variables

Previous NHL therapies will be reviewed and assessed by a [REDACTED] medical monitor. The review will be conducted in line with the [REDACTED] SOP-MA-11 on data from the eCRF module 'Previous NHL therapies' once prior to the analysis. Clarifications on the data may be addressed by the [REDACTED] medical monitor to the sites directly using the Remote Data Capture portal of the database or via the responsible CRA/CM. The recorded NHL therapies will be grouped into lines of therapies taking into account all therapeutic procedures recorded (pharmacological treatment, surgery and radiotherapy), the chemotherapy regimens, response data and feedback to clarifications by the sites. Induction, consolidation, stem cell collection, preparative regimen including transplantation, and maintenance will be considered a single line

Statistical Analysis Plan Final Version 4.0

of therapy. In addition systemic therapies [systemic pharmacology therapy, systemic radiotherapy (RT), radio-immunotherapy (RIT), and stem cell transplantation (SCT),] will be identified indicating the type of therapy (chemo, immuno, immune-chemo, SCT, RIT, systemic RT). Furthermore rituximab containing regimens will be identified and grouped into subgroups (single agent, R-CHOP or R-CHOP-like and other). The outcome of the review will be recorded in a table indicating the lines of therapy, the systemic therapies, the types of therapy and the rituximab-containing regimens) and will be reviewed by a second medic. Adjudication of cases with discrepant assessments will be performed by discussing the case with both medics involved. If the assessments remain discrepant the final decision about the case lies with the sponsor. The data and outcome of the review and related correspondence will be documented and filed in the TMF.

The following variables will be derived from this assessment:

- Number of prior lines of therapy (as continuous variable and as number of patients with 1, 2, 3, or > 3 prior lines)
- Number and type of prior systemic therapies (as continuous variable and as number of patients with 1, 2, 3, or > 3 prior therapies)
- Number (%) of patients with prior rituximab containing regimens, in total and broken down as:
 - single agent rituximab
 - R-CHOP or R-CHOP-like (R-CHOP, R-CHOEP, R-CVP, R-GEMOx, R-THP-COP)
 - Other (purine analog + rituximab, R-bendamustine, R-HyperCVAD, R -ICE, R-DHAP, R-EPOCH, R-COMP, etc.)
- Number (%) of patients with previous therapies by type (surgery, local radiation therapy, chemotherapy, immunotherapy, immune-chemotherapy, systemic radiation therapy, stem cell transplantation, or any other previous therapy)
- Previous NHL Therapies will be coded using the current version of the WHO Drug Dictionary Enhanced (WHO-DDE). Surgical and medical procedures will be coded using MedDRA. The following variables will be derived from the eCRF directly:
- Response to last therapy before study inclusion, in categories CR, PR, SD, PD, and unknown
- Response to last rituximab-containing therapy line (broken down into any rituximab-containing therapy, rituximab containing monotherapy, and rituximab-containing

combination treatments) before study inclusion, in categories CR, PR, SD, PD, and unknown

- Classification of patients as rituximab refractory (no response or response lasting < 6 months to a prior rituximab-containing therapy; patients will be considered refractory if they are refractory to any rituximab-containing regimen, even if they had responded to another rituximab-containing regimen)
- Duration of response to last therapy, as a continuous variable (in months) and as number and % (and cumulative number and %) of patients with responses of < 6 months, 6–12 months, > 12 months, and unknown duration (if the end date of the duration of response to last therapy is not specifically recorded, it will be assumed to be the date of screening for the present study)

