8.1 Inclusion Criteria

1. Patients are male or female ≥ 18 years of age.
2. Patients have a histologically confirmed diagnosis according to the Revised European American lymphoma/World Health Organization (REAL/WHO) classification, of the following B-cell lymphomas:
 - a. FL
 - b. Other indolent NHL (eg, MZL/MALT) (see section 17.7)
 - c. DLBCL
 - d. MCL

NOTE: For transformed lymphomas, the subtype at screening (not at initial diagnosis) is relevant for the assignment to the respective subtype.

3. Patients' NHL must have progressed after at least 1 prior rituximab-containing regimen.
4. Patients have at least one site of measurable disease by magnetic resonance imaging (MRI) or computed tomography (CT) scan defined as at least one lesion that measures at least 1.5×1.5 cm,

Exception:

For patients with MCL only, patients with nonmeasurable disease but evaluable sites (bone marrow, spleen, peripheral blood, gastrointestinal tract) can be enrolled.

5. Patients who have previously received an autologous stem cell transplantation must be at least 4 weeks post-transplant before study drug administration and must have exhibited a full haematological recovery.
6. Patients must have discontinued previous monoclonal antibody therapy (except rituximab) or radioimmunotherapy administration for at least 60 days before study drug administration.
7. Patients should be off rituximab for at least 14 days before the screening visit and be confirmed to have either no response or have disease progression after rituximab treatment.
8. Patients with DLBCL had a positive [^{18}F]fluorodeoxyglucose-positron emission tomography (FDG-PET) scan at baseline (Cheson 2007 response criteria).
9. Patients have a life expectancy of > 3 months.
10. Patients must have an Eastern Cooperative Oncology Group (ECOG) performance status of < 3 .

11. Patients must meet the following laboratory criteria at screening:
 - a. Absolute neutrophil count (ANC) $\geq 1.0 \times 10^9/L$
 - b. Platelet count $\geq 75 \times 10^9/L$ without previous transfusion within 10 days of first study drug administration
 - c. Hemoglobin ≥ 8.0 g/dL (may have been transfused)
 - d. Serum creatinine < 2.0 x upper limit of normal (ULN)
 - e. Total bilirubin $\leq 2.0 \times$ ULN
 - f. Alanine transaminase (ALT) and aspartate aminotransferase (AST) $\leq 2.5 \times$ ULN

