10.9.2 Relevant Medical History and Current Medical Conditions

Relevant medical history and current medical conditions will be recorded until the start of the study drug administration.

The medical history of NHL should be documented in detail. This should include the date of first diagnosis, details on NHL subtype, previous treatments, and best response and duration of response to these treatments. Any previous therapy (eg, chemotherapy, immunotherapy, or radiation therapy) for the NHL-specific therapy should be recorded in the eCRF.

Also, examinations leading to the diagnosis of the latest progression of NHL should be documented in the patient's source documents. This may include, for example, results of laboratory examinations, imaging results, or clinical symptoms related to the NHL. The baseline assessment of the lymphoma should include a staging.

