9.3 Subgroup analyses

Both ORR and PFS will be evaluated for the following subgroups:

- ORR and PFS will be presented in subgroups defined by prognostic index scores, dichotomised as high risk and low risk as described in section 7.3.2.
- ORR and PFS will be presented by FcγR subgroups as described above.
- ORR and PFS will also be presented by duration of response (≤ 12 months or > 12 months) to previous treatment.
- ORR and PFS will also be presented by the number of prior therapy lines (as 1, 2, 3, or > 3).
- ORR and PFS will be presented for the category of patients with Follicular lymphoma (FL) or other indolent lymphoma (as one group).

In addition, PFS only will be presented in further subgroups as follows:

- Baseline ECOG status (0–1 vs. 2 or more)
- Age group (<65 vs. ≥ 65)
- Number of prior therapy lines (as 1, 2, 3, vs >3)

Statistical Analysis Plan Final Version 4.0

- Baseline NK cells number (<100 NK cells/ μl vs ≥ 100 NK cells/ μl)
- Baseline NK cells number (<100 NK cells/ μl vs. ≥ 100 NK cells/ μl): pooled analysis across all NHL subtypes (i.e., DLBCL, FL, MCL, other indolent NHL)
- Baseline NK cells number (<100 NK cells/ μl vs. ≥ 100 NK cells/ μl) split by DLBCL and FL+iNHL patients (FL+iNHL patients represent one group). Thus, MCL patients will be excluded from the analysis.
- Baseline CD16 expression ($< 60,000$ ABCs/NK cell) vs. $\geq 60,000$ ABCs/NK cell)
- Baseline CD16 expression ($< 60,000$ ABCs/NK cell) vs. $\geq 60,000$ ABCs/NK cell): pooled analysis across all NHL subtypes (i.e., DLBCL, FL, MCL, other indolent NHL)
- Baseline CD16 expression ($< 60,000$ ABCs/NK cell) vs. $\geq 60,000$ ABCs/NK cell): split by DLBCL and FL+iNHL patients (FL+iNHL patients represent one group). Thus, MCL patients will be excluded from the analysis.
- Rituximab refractoriness (Rituximab-refractory vs. not Rituximab-refractory; see definition below)
- Rituximab refractoriness (Rituximab-refractory vs. not Rituximab-refractory; see definition below): pooled analysis across all NHL subtypes (i.e., DLBCL, FL, MCL, other indolent NHL)
- Rituximab refractoriness (Rituximab-refractory vs. not Rituximab-refractory; see definition below): pooled analysis across all NHL subtypes excluding MCL (i.e., DLBCL, FL, other indolent NHL)

Rituximab refractoriness is defined as follows: no response (i.e., CR or PR) at all, or relapse within 6 months after completion of any rituximab-containing treatment regimen.

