For the PFS subgroup analyses an estimate of the hazard ratio and a corresponding 95% confidence interval will be calculated using a Cox proportional hazards model with only one covariate in the model.

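### An unrecorded end of prior response is set to the screening date, its latest possible value, which can place short prior responders in the over-12-months subgroup for ORR and PFS

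*SAP*

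**What the plan says.** SAP 7.3.1 derives the duration of response to the last therapy before inclusion, both in months and in categories. The final categories are "> 12 months, and unknown duration". The same bullet adds a rule: "if the end date of the duration of response to last therapy is not specifically recorded", then "it will be assumed to be the date of screening for the present study".

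The variable is used again in SAP 9.3: "ORR and PFS will also be presented by duration of response (≤ 12 months or > 12 months) to previous treatment". For the PFS subgroups, "an estimate of the hazard ratio and a corresponding 95% confidence interval will be calculated using a Cox proportional hazards model" with a single covariate.

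Four other places bear on the rule:
- Protocol 8.1, criterion 3, requires that the "NHL must have progressed after at least 1 prior rituximab-containing regimen". Criterion 7 requires patients to "be confirmed to have either no response or have disease progression after rituximab treatment".
- Protocol 8.4 lists, among the grounds for re-screening, an earlier screen failure because the disease had not progressed or relapsed.
- Protocol 10.9.2 asks sites to record "previous treatments, and best response and duration of response to these treatments", and to keep the examinations that diagnosed the latest progression in the source documents.
- Protocol 14.11 says missing values are not replaced by estimates. SAP 7.1 allows exceptions where the SAP specifies them. SAP 12, which lists changes from the planned analysis, does not mention this one.

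**The concern.** The screening date is not a neutral guess at when a prior response ended. A patient still in response would not be enrolled, so for an enrolled responder the response was already over. The rule therefore assigns the longest duration that the calendar allows and counts the interval from progression to screening as time in response.

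The derived value feeds an efficacy comparison as well as a baseline table. If a short prior response goes with a worse outcome on study, moving short responders into the over-12-months group dilutes that group and shrinks the contrast in ORR and PFS. No sensitivity analysis of the rule is planned, and the reader of the subgroup table would not know how many durations were imputed.

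**Working it through.** The plan states no figure for this rule, so there is nothing to reproduce. The check covers direction first, then size.

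**Direction.** Let T be the true duration in months and g ≥ 0 the gap from end of response to screening. The imputed duration is T + g, which is never less than T. A patient changes group exactly when T ≤ 12 and T + g > 12, that is, when 12 − g < T ≤ 12. Movement from over 12 to 12 or less is impossible.

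*Example with assumed dates:* response from 15 January to 15 September 2012, screening on 15 June 2013. With the SAP's factor of 30.4375 days per month:
- true duration: 244 / 30.4375 = 8.0 months
- imputed duration: 517 / 30.4375 = 17.0 months

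The patient moves from the lower to the upper group.

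**Share that crosses.** Among patients with a missing end date and T ≤ 12, the share moved is [F(12) − F(12 − g)] / F(12). I assume exponential durations with median m, so F(t) = 1 − 2^(−t/m), and the same gap for everyone. Neither assumption comes from the documents. For m = 9 and g = 6: (0.603 − 0.370) / 0.603 = 38.6%.

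| Gap g | m = 6 | m = 9 | m = 12 |
|---|---|---|---|
| 1 month | 4.1% | 5.3% | 5.9% |
| 3 months | 13.8% | 17.1% | 18.9% |
| 6 months | 33.3% | 38.6% | 41.4% |
| 12 months | 100% | 100% | 100% |

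**Effect on ORR.** Assumed: 20 patients truly over 12 months with ORR 40% (8 responders), 20 patients at 12 months or less with ORR 20%, and five of the latter with no end date. If k of the five cross, and they respond at their group's 20%, the over-12-months ORR reads (8 + 0.2k) / (20 + k).

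- g = 3: k = 5 × 0.138 to 5 × 0.189 = 0.69 to 0.95, giving 39.3% to 39.1%.
- g = 6: k = 5 × 0.333 to 5 × 0.414 = 1.67 to 2.07, giving 38.5% to 38.1%.
- All five cross: (8 + 1) / 25 = 36%.

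The lower group stays at 20% in expectation, so the 20-point contrast becomes about 19, 18 and 16 points respectively. For scale, the exact 95% interval for 8/20 is about 19% to 64%.

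**The case against.** **The entry criteria do not name the last therapy.** Criteria 3 and 7 concern rituximab, and the last therapy may not have contained it. This is correct, but the trial population is relapsed or refractory, and Protocol 8.4 treats disease that has not progressed or relapsed as a reason for screen failure. Together these support active disease at screening. Protocol 8.4 also suggests that some patients are screened soon after progression, which would make their gap small.

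**Missing dates may be few.** Protocol 10.9.2 asks for the duration of each prior response. SAP 7.3.1 provides a medical review of prior therapies before analysis, with site clarifications and a second medical reader. These steps should reduce missingness but do not guarantee an end date, and the rule exists because gaps are expected.

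**The split is descriptive.** Protocol 14.10 plans no inferential testing. In the example the error shrinks the contrast and does not create one, and the shift is small beside the sampling error. This stands and limits the importance of the point.

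**Stronger readings to avoid.** A reader might infer that every imputed patient lands in the over-12-months group. Only those with a true duration of 12 months or less, and a response that began more than 12 months before screening, change group. A reader might also infer that the unknown category is left almost empty. It can still hold patients with no response start date or with unknown response to the last therapy.

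**Conclusion.** The point holds. The rule assigns an upper bound, and its errors can only move patients from 12 months or less to over 12 months. The same bullet already offers an unknown category that would avoid this.

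The size cannot be determined, because the documents give neither the proportion of missing end dates nor the gap to screening. Under the assumptions above, the over-12-months ORR falls from 40% to about 39% or 38% for gaps of 3 or 6 months. The 36% figure needs all five patients to cross, which is certain only for gaps of about 12 months or more.

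A reader might infer that the main efficacy result is at risk, but the documents do not support that. The effect is confined to the baseline summary of prior response duration and one descriptive subgroup split. The primary ORR by subtype, its confidence interval and the Stage 1 futility rule do not use this variable. This is a change worth making, not one on which the trial's conclusions turn.

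**What to change.** Amend SAP 7.3.1 as follows:

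1. Where the end date is missing, query the site for the progression date through the clarification route already in that section. The source documents should hold it under Protocol 10.9.2.
2. Code dates still missing as unknown duration, and leave those patients out of the two-level split in SAP 9.3.
3. Report how many patients this affects.
4. Keep the screening-date rule only as a sensitivity analysis, and record the change in SAP 12.

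The start of the next recorded therapy would not serve as a substitute date. The variable concerns the last therapy before inclusion, so the next treatment is the study drug itself.

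The cost is a short change to the SAP text, some site queries, and the loss of a few patients from one subgroup split.
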